#### EXTRAPOLATION MODELLING

The trial is designed to estimate differences in costs and recurrence rates over five years. However, the relative cost-effectiveness of the two forms of management needs an assessment of costs and benefits over a longer time horizon (out-with the feasibility of a trial). Furthermore, the economic importance of any difference in recurrence rates demonstrated in the trial needs to be estimated in terms of longer-term costs and a more general measure of benefit, such as quality-adjusted life years. Decision modelling will be employed for this extrapolation, together with published clinical, economic and epidemiological data (Sonnenberg and Beck, 1993). This work will build upon modelling currently being undertaken at the Centre for Health Economics alongside the ALMANAC Trial. The model would take the form of a long-term Markov model representing disease progression following a loco-regional recurrence. Some data collected in the trial will be important for this modelling, in particular the EQ-5D data which will facilitate estimates of utilities associated with key states in the model. The ultimate objective of the extrapolation modelling would be to estimate differential costs and quality-adjusted life years (QALYs) for both forms of management being assessed in the trial, but over a time horizon of women's lifetimes.

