#### 7.2 TIMING OF QUALITY OF LIFE ASSESSMENTS AND ADMINISTRATION OF QUESTIONNAIRES

Patients will be asked to complete questionnaires at the following time intervals:

-	HADS	pre-randomisation
		8 weeks post randomisation
		6 and 12 months post initial surgery.

- FACT-B pre-randomisation 8 weeks post randomisation 6 and 12 months post initial surgery.
- Ad hoc questionnaire (to examine concerns about tumour recurrence) 8 weeks post randomisation 6 and 12 months post initial surgery.

-

EQ-5D

pre-randomisation8 weeks post randomisation6 and 12 months post initial surgery.

The first set of questionnaires should be given to the patient after written informed consent has been given, and prior to randomisation. It is essential that the questionnaires are completed by the patient before they are informed of the randomisation allocation, to ensure that all patients complete the questionnaires without any knowledge of any further investigations or treatment changes. The completed questionnaires should be returned to the CTRU. In order to maximise compliance, all subsequent questionnaires will be sent to the patient's home address by the CTRU. The CTRU will endeavour to check the patient's current status with the relevant research nurse before sending questionnaires. Pre-paid envelopes will be provided for the return of questionnaires. Patients not responding within two weeks will be sent a reminder letter. Patients not returning two consecutive sets of questionnaires will not be sent any further questionnaires. A letter of thanks will be sent to patients who return a set of completed questionnaires.

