#### 9.1.2 ECONOMIC EVALUATION

The economic evaluation from a societal perspective of the two principles under investigation, will include within-trial cost-effectiveness relating differential costs to ipsilateral breast tumour recurrence rate out to 60 months; and an extrapolated cost-effectiveness analysis, where longer term costs and quality-adjusted survival will be modelled on the basis of any difference in trial estimates of recurrence.

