#### **11.1.2 HEALTH ECONOMICS ASSESSMENT**

The economic evaluation will take the form of a cost-effectiveness analysis and will consist of two parts. The first will be a within-trial comparison of the costs of the two forms of management related to differences in recurrence rates over a five-year period. The second part will involve the use of decision modelling and published data to extrapolate any differences in recurrence rates at five years to longer-term costs and quality-adjusted life expectancy.

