Estimating effects. The key measure of effect for the within-trial cost-effectiveness analysis will be recurrence rates over five years. The within-trial analysis will, therefore, relate differential (societal) costs to differential recurrence rates. Within the trial, patients will also be asked to complete the EQ-5D instrument – a preference-based measure of health status - which will facilitate patient-specific health state values over time (Kind, 1996). Whilst the use of the EQ-5D will facilitate a valuable single-index measure of health within the trial, its main use for the economic evaluation will be to provide health state values (utilities) for the extrapolation modelling (see (i) below). The within-trial cost-effectiveness analysis will include discounting of costs and effects (Department of Health, 1995), adjustment for differential follow-up (Lin et al, 1997) and a stochastic analysis using cost-effectiveness acceptability curves (Van Hout et al, 1994).

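### The QALY side of the primary economic endpoint has no direct path for quality-of-life effects of avoided re-operations or MR-prompted larger surgery

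*Combined protocol and SAP*

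**What the plan says.** Three places describe the lifetime analysis, and they agree.

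- Section 9.1.2, under primary endpoints: "longer term costs and quality-adjusted survival will be modelled on the basis of any difference in trial estimates of recurrence".
- Section 11.1.2, opening paragraph: the second part of the evaluation will use decision modelling and published data to "extrapolate any differences in recurrence rates at five years to longer-term costs and quality-adjusted life expectancy".
- Section 11.1.2, Extrapolation modelling: "The model would take the form of a long-term Markov model representing disease progression following a loco-regional recurrence". The aim is to "estimate differential costs and quality-adjusted life years (QALYs) for both forms of management being assessed in the trial", over the women's lifetimes.

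The within-trial analysis in section 11.1.2 relates cost differences to differences in five-year recurrence. It also collects EQ-5D, but "its main use for the economic evaluation will be to provide health state values (utilities) for the extrapolation modelling". It specifies no within-trial QALY and no comparison of EQ-5D between arms. The extrapolation text says that some trial data will matter for the model, "in particular the EQ-5D data which will facilitate estimates of utilities associated with key states in the model", without naming those states.

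Section 7.2 schedules EQ-5D at the same times as FACT-B: "pre-randomisation 8 weeks post randomisation 6 and 12 months post initial surgery". Nothing is scheduled later. Surgical procedures, hospital stays and productivity losses are all costed (section 11.1.2, Estimating costs).

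**The concern.** The trial is sized on repeat operation or mastectomy (section 10.1), and section 9.2.5 defines and tracks MR-prompted surgery that histopathology shows to have been larger than needed. Both can affect how a woman feels and functions without affecting recurrence. In the plan both count as costs, but neither has a stated direct entry on the QALY side.

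The one stated driver of QALYs is recurrence, and section 11.2.1 expects the trial to be underpowered for it. A cost per QALY built this way could therefore rest on an imprecise recurrence difference and leave out a first-year quality-of-life difference that the trial measures in both arms. The omission could also be one-sided. If larger surgery lowers ipsilateral recurrence (an assumption), MR-prompted mastectomies would enter as a QALY gain and their quality-of-life cost would not be counted.

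**Working it through.** **1. The plan's own figure.** Inputs from section 10.1: 15% against 10%, 90% power, two-sided 5%, chi-squared test without continuity correction. Allocation is 1:1 (section 3).

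n per arm = [1.960 × √(2 × 0.125 × 0.875) + 1.2816 × √(0.15 × 0.85 + 0.10 × 0.90)]² / 0.05² = 918 after rounding up, so 1836 in total against the stated 1840. At 920 per arm the power is 0.901. The sample size is not in dispute. It shows which effect the trial is built to see: 0.05 × 920 = 46 fewer women with a repeat operation or mastectomy in the MR arm.

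**2. What the written rule implies for QALYs.** Let Δr be the recurrence difference (no MR minus MR) and L the QALYs lost per recurrence in the Markov model. Simplified, the plan gives

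incremental QALYs = Δr × L.

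If recurrence is the same in both arms, in rate and timing, Δr = 0 and the result is 0 for any L. No EQ-5D difference at 8 weeks, 6 months or 12 months changes that, because EQ-5D enters only through the state utilities that make up L. A calculation starting at randomisation would instead be

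incremental QALYs = (difference in QALYs over the first 12 months) + (recurrence-driven difference after 12 months).

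The first term is missing from the plan.

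**3. Scale, as illustration only.** The documents give no utility decrement, duration, conversion rate or QALY loss per recurrence. Every such value below is an assumption. Results are undiscounted and per woman randomised.

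- Avoided re-operations: 0.05 × decrement × duration. Low: 0.05 × 0.05 × 1/12 = 0.0002. High: 0.05 × 0.20 × 6/12 = 0.005.
- MR-prompted larger surgery, first year only: share converted × decrement × 1 year. Low: 0.01 × 0.01 × 1 = 0.0001. High: 0.10 × 0.05 × 1 = 0.005.
- The same, lasting 20 years: high 0.10 × 0.05 × 20 = 0.10.
- Recurrence term: Δr × L. Low: 0.005 × 0.5 = 0.0025. High: 0.02 × 3 = 0.06. It is 0 if recurrence does not differ.

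The first two terms have opposite signs and may partly cancel. The third does not subtract later mastectomies that MR might prevent, and discounting would shrink it. Under these assumptions the first-year terms are small beside a real recurrence difference, but they are the whole QALY result if there is none. A long-lasting decrement could match or exceed the recurrence term, but the trial's EQ-5D cannot show whether it lasts.

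**The case against.** The strongest reply is that section 11 is an outline. The model is described conditionally, its states are not listed, and it builds on other modelling work that is not in the documents. EQ-5D ends 12 months after initial surgery, so most of it will describe women without recurrence. Its stated main use is still to supply utilities for this model, and the aim is lifetime QALYs for both arms. That suggests some time before recurrence is modelled.

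Much of this stands, and it rules out several stronger readings that a reader might infer:

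- *That surgery cannot change the QALY result.* It can act through recurrence. The Background links recurrence to resection margins and multi-focal disease.
- *That the model contains no surgery-type state.* The documents list no states, so they fail to specify one but do not exclude one.
- *That the economic endpoint ignores re-operations and mastectomies.* Their costs are counted. The gap is on the QALY side.
- *That inappropriate mastectomy is documented as the main harm, at up to 28%.* The Background takes that figure from a preliminary report, which the reference list gives as conference proceedings on invasive lobular carcinoma. It suggests that slower imaging may have added to false positives. The plan makes the outcome secondary.
- *That the omission would reverse the result.* This depends entirely on assumed decrements and durations.

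What the reply does not remove is the stated rule. All three descriptions name the recurrence difference as the basis for QALYs, and the within-trial analysis uses the same effect measure. A pre-recurrence state with the same utility and occupancy in both arms would still give a zero difference when recurrence is equal. Leaving the structure of a primary endpoint open also lets it be settled after the arm-level results are known.

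**Conclusion.** The point holds in a limited form. Sections 9.1.2 and 11.1.2, as written, give no direct QALY effect to avoided re-operations or to MR-prompted larger surgery. With equal recurrence, incremental QALYs are zero whatever EQ-5D difference is observed. This conclusion rests on reading the three descriptions as the full rule for the QALY comparison.

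The size of the omission cannot be determined from the documents. The ranges above rest on assumed values; they show that the omitted terms could be negligible or could matter, and do not show which. The change is still worth making because it concerns a primary endpoint, the stated driver is one for which low power is expected, and the data needed are already collected in both arms.

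**What to change.** In sections 9.1.2 and 11.1.2:

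1. State that the QALY calculation starts at randomisation.
2. Compute each woman's QALYs to 12 months as the area under her EQ-5D values (baseline, 8 weeks, 6 and 12 months). Use actual dates, because the 8-week form is timed from randomisation and the last two from initial surgery.
3. Compare these QALYs by randomised arm, adjusted for baseline EQ-5D, and report the difference with a 95% confidence interval.
4. Add this difference to the recurrence-driven extrapolation. Count QALY losses from recurrence only after 12 months, so that early recurrences, which already affect first-year EQ-5D, are not counted twice.
5. Present pre-recurrence utilities by type of surgery only as a sensitivity analysis over a stated range of decrement and duration. Surgery received is not randomised and is linked to disease extent, and EQ-5D stops 12 months after initial surgery.
6. List the model states before arm-level results are seen.

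No new data are needed: EQ-5D (section 7.2), type of operation (section 8.5) and further surgery (section 8.8) are already collected. The cost is a little more analysis, with missing EQ-5D to be handled, and some added noise in incremental QALYs from the first-year difference.

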#### **11.2** SECONDARY ENDPOINTS

#### **11.2.1 RECURRENCE RATE**

The analysis of time to ipsilateral breast tumour recurrence will be conducted up to five years post completion of radiotherapy (i.e. when there is at least five years follow-up for all patients). Cox's Proportional Hazards Model will be fitted. Adjustment will be made for the stratification variables and other covariates that are identified as being prognostic of outcome. Treatment effects will be

expressed as hazard ratios. Point estimates will be reported with 95% confidence intervals without formal hypothesis testing, as it is anticipated that the trial will have insufficient power to detect differences between the trial arms in recurrence rates.

#### **11.2.2** Chemotherapy/radiotherapy interventions

The proportion of women in the two trial arms who have subsequent chemotherapy/ radiotherapy interventions will be compared using a chi-squared test without continuity correction. 95% confidence intervals will be reported. Adjustments will be made for the stratification variables and other covariates that are identified as being prognostic of outcome. The adjusted analysis will be reported with the unadjusted analysis.

#### **11.2.3** QUALITY OF LIFE AND PATIENT SATISFACTION

The six sub-scales of FACT-B (physical well-being, social well-being, emotional well-being, functional well-being, relationship with doctor, breast cancer concerns) and two sub-scale scores for HADS (anxiety, depression) will be transformed to a percentage of the maximum score for each sub-scale. Point estimates and 95% confidence intervals will be reported for the percentage means for each of the sub-scale scores at 6 months. Regression models will be used to adjust for baseline scores and other important covariates. Missing data patterns will be examined carefully. Methods that account for informatively missing data will be used if necessary.

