### 7. QUALITY OF LIFE AND ECONOMIC EVALUATION

#### 7.1 QUALITY OF LIFE ASSESSMENT

In order to evaluate the impact of the investigations and treatment on the quality of life (QOL) of the women involved in the trial, questionnaires will be completed by the patients.

The Functional Assessment of Cancer Therapy, Breast Cancer Version (FACT-B) will be used to evaluate the impact on physical well-being, social well-being, emotional well-being, functional well-being and breast cancer concerns. FACT-B comprises the FACT-General (Cella et al, 1993) and ten

specific items related to breast cancer (Brady et al, 1997). The questionnaire has been developed over a number of years and has been used in several major UK trials (Walker et al, 1999). Satisfactory reliability and validity have also been demonstrated (Cella et al, 1993; Brady et al, 1997). For the purpose of this study the question GE3 "I am losing hope in the fight against my illness" has been removed. This does not affect the scalar structure of the questionnaire.

Anxiety and depression will be assessed using the Hospital Anxiety and Depression Scale (HADS) (Zigmond and Snaith, 1983). The HADS is a widely used questionnaire which has been shown to be reliable and valid in the detection of clinically significant anxiety and depression in patients with cancer (Razavi et al, 1990; Hopwood et al, 1991; Ibbotson et al, 1994). In addition, HADS scores have been shown to be sensitive to the effects of breast screening and recall within the context of the NHS programme (Walker et al, 1994, Gilbert et al, 1998).

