#### 9.2.3 QUALITY OF LIFE AND PATIENT SATISFACTION

Quality of life as assessed by the FACT-B, and anxiety and depression as assessed by the HADS, at 8 weeks post randomisation and 6 and 12 months post surgery. Concerns about tumour recurrence post-operatively will be assessed by an ad-hoc questionnaire at 8 weeks post randomisation and 6 and 12 months following surgery.

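### FACT-B and HADS are endpoints at 8 weeks, 6 and 12 months, but section 11.2.3 plans estimates at 6 months only; its FACT-B sub-scale list also differs from section 7.1

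*Combined protocol and SAP*

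**What the plan says.** All references are to the combined protocol and SAP.

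- **Endpoint (9.2.3).** FACT-B and HADS are assessed "at 8 weeks post randomisation and 6 and 12 months post surgery".
- **Schedule (7.2).** The entry for FACT-B reads "FACT-B pre-randomisation 8 weeks post randomisation 6 and 12 months post initial surgery". HADS has the same four times.
- **Analysis (11.2.3).** "Point estimates and 95% confidence intervals will be reported for the percentage means for each of the sub-scale scores at 6 months". The section adds regression adjustment for baseline scores and other covariates, an examination of missing-data patterns, and methods for informative missingness should they be needed.
- **General rules (11).** The section is headed as an outline. Inference uses available data, with sensitivity analyses when data are missing. Formal tests are confined to the primary endpoints.
- **FACT-B content.** Section 7.1 says the instrument covers "physical well-being, social well-being, emotional well-being, functional well-being and breast cancer concerns". The list of six sub-scales in section 11.2.3 ends with "functional well-being, relationship with doctor, breast cancer concerns".

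**The concern.** The endpoint has three times and the analysis has one. No section explains why 6 months was chosen or calls it the key time.

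The 8-week assessment matters most here. Under section 5.2.1, MR imaging, any extra biopsy and any revision of the surgical plan all fall between randomisation and initial surgery. Of the three later assessments, 8 weeks is the closest to these events. The change log shows that the early assessment was re-timed by amendment and not removed, so it was wanted.

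A difference in anxiety or well-being that appears at 8 weeks and has faded by 6 months would be collected but would have no pre-specified place in the report. The same goes for a difference that appears only at 12 months. Because the trial is open, leaving those times to be decided later also allows selective reporting.

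The sub-scale mismatch is a separate point of consistency: as written, a reader cannot tell how many FACT-B scores will be reported.

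**Working it through.** **1. The plan's own figure.** The documents give no effect size, standard deviation or power for quality of life. The one stated figure is the total of 1,840 in section 10.1, from 15% versus 10%, 90% power, 5% two-sided, chi-squared without continuity correction.

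n per arm = [1.960 × √(2 × 0.125 × 0.875) + 1.2816 × √(0.15 × 0.85 + 0.10 × 0.90)]² / 0.05² = (0.9167 + 0.5977)² / 0.0025 = 917.3, rounded up to 918.

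The total is 1,836, which agrees with 1,840. Nothing below changes it.

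**2. Times with and without a planned estimate.**

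| Time | Endpoint (9.2.3) | Collected (7.2) | Estimate planned (11.2.3) |
|---|---|---|---|
| Before randomisation | no | yes | used as covariate |
| 8 weeks | yes | yes | none stated |
| 6 months | yes | yes | yes |
| 12 months | yes | yes | none stated |

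Two of the three endpoint times have no stated analysis. Across the two instruments that is 4 of 6 post-randomisation assessments (67%). Counting baseline as used, it is 4 of 8 (50%).

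**3. Number of estimates.** Six FACT-B sub-scales plus two HADS sub-scales make 8. At one time that is 8 estimates; at three times, 8 × 3 = 24. If relationship with doctor is not in the questionnaire given, the figures are 7 and 21.

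**4. How precise a single-visit estimate would be.** With n women per arm returning the form and correlation r between baseline and follow-up score, the half-width of the 95% interval for the adjusted arm difference is 1.96 × √(2/n) × √(1 − r²), in standard deviations. The documents give neither r nor the return rate, so both are assumed.

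| Return (n per arm) | r = 0.3 | r = 0.5 | r = 0.7 |
|---|---|---|---|
| 100% (920) | 0.087 | 0.079 | 0.065 |
| 75% (690) | 0.101 | 0.091 | 0.075 |
| 50% (460) | 0.123 | 0.112 | 0.092 |

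Across this range an 8-week or 12-month difference would be known to within about 0.07 to 0.12 standard deviations. The unplanned visits are therefore informative in their own right.

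**5. Sub-scale lists.** Four well-being areas and breast cancer concerns appear in both sections. Relationship with doctor appears only in section 11.2.3. Section 7.1 reports one item removed, GE3, and says the scale structure is unaffected. That does not explain the difference.

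**The case against.** The strongest reply is that section 11 is an outline and section 11.2.3 does not say that other times are excluded. That is correct: the 8-week and 12-month analyses are unspecified, not ruled out. Quality of life is also secondary and estimation only, so no primary conclusion depends on it. Both points limit the weight of the concern. They do not close the gap, because the endpoint definition names three times and the analysis text names one.

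A reader might infer more than the documents support, in five ways.

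- **That most of the data go unused.** This holds only for post-randomisation FACT-B and HADS scores. Baseline scores serve as covariates, and EQ-5D goes to the economic evaluation (11.1.2).
- **That missing data are ignored.** Section 11.2.3 says missing-data patterns will be examined and suitable methods used if needed, and section 11 promises sensitivity analyses. The wording is general, but the issue is addressed.
- **That the mailing rule in section 7.2 undermines the 6-month estimate.** The rule is "Patients not returning two consecutive sets of questionnaires will not be sent any further questionnaires". Missing the 8-week and 6-month sets stops only the 12-month set. The 6-month set could be lost only if baseline and 8 weeks were both missing, and baseline forms are handed over in person before allocation is known. Changing the rule trades burden on non-responders against completeness, and this point does not call for it.
- **That a three-visit average would show the size of the loss.** Such an average is a different estimand from the 6-month effect and would dilute a difference confined to 8 weeks. With complete data, a repeated-measures model gives essentially no precision gain for the 6-month difference itself.
- **That a relationship-with-doctor score cannot be computed, or that the mismatch leaves data unused.** The documents do not settle which list matches the questionnaire given, and an extra name on a list leaves no data unused.

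**Conclusion.** The concern holds in a limited form. Two of the three times in the FACT-B and HADS endpoint, including the one nearest MR imaging, biopsy and surgery, have no pre-specified analysis. An early or late difference could be overlooked or reported selectively. This follows from comparing sections 7.2, 9.2.3 and 11.2.3 and needs no numerical assumption. The precision range does rest on assumed correlations of 0.3 to 0.7 and assumed return of 50% to 100%.

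The sub-scale lists in sections 7.1 and 11.2.3 disagree by one entry; this is a separate inconsistency.

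The primary endpoint, the sample size and the error rate of the formal tests are unaffected. The change should be made, but the trial's main conclusion does not depend on it.

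**What to change.** - **Model.** In section 11.2.3, specify for each sub-scale a mixed model for repeated measures at 8 weeks, 6 and 12 months, with arm, visit, arm-by-visit interaction, baseline score and the minimisation factors. Report the arm difference with its 95% interval at each visit. If 6 months is meant to be the key time, say so.
- **Missing data.** The model also uses the 8-week and 12-month answers of women who missed the 6-month form, on the assumption that data are missing at random given what was observed. Keep the methods for informatively missing data already in section 11.2.3 as sensitivity analyses.
- **Consistency with section 11.4.** That section gives primacy to unadjusted analyses, including for secondary endpoints. Either show the unadjusted difference at each visit alongside, or state there that the baseline-adjusted model leads for quality of life.
- **Sub-scales.** Check the questionnaire actually given and make sections 7.1 and 11.2.3 list the same sub-scales.

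The cost is plan wording and a standard model on data already scheduled for collection. The downside is 24 estimates to present instead of 8. If no true difference exists anywhere, the expected number of 95% intervals excluding zero rises from 8 × 0.05 = 0.4 to 24 × 0.05 = 1.2, so the report should describe them as estimates. No formal tests are added, because section 11 confines testing to the primary endpoints.
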